3.1 Primary Objectives

There are three domains to this study design contributing to the primary objectives (**figure 1**).

Clinical screening domain (part 1):

Among the London Mongolian community:

- Estimate the prevalence the number of people living with chronic viral hepatitis (HBV, HCV and HDV).
- Estimate the prevalence MASLD and presence of metabolic risk factors (obesity, hypertension, diabetes and dyslipidaemia).
- Develop community engagement and develop a stakeholder group to support the establishment of a screening and research programme for chronic viral hepatitis infection (HBV, HCV, HDV).
- To raise awareness of liver health, in particular chronic viral hepatitis (HBV, HCV and HDV) and metabolic dysfunction-associated steatotic liver disease (MASLD)

Laboratory research domain (laboratory test, part 2):

Among the London Mongolian community:

- Compare lipidomic profiles between PLWHB and MASLD, PLWHB only, people living with MASLD only and people without CHB or MASLD to investigate the interplay between the two major global causes of liver disease.
- Identify demographic, clinical and laboratory factors (e.g. viral sequencing, host immune and lipidomic profile, host HLA sequencing) associated with liver disease among people living with chronic viral hepatitis.

Qualitative domain (part 3):

Among the London Mongolian community:

- To understand attitudes, facilitators and barriers to testing and accessing healthcare for chronic viral hepatitis.

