- For those who test positive for HIV, HBV, HCV or HDV we will contact their specialist care provider before the end of the study (~12 months post diagnosis) to ascertain clinic attendance, which will allow us to understand linkage and retention in specialist care.
- Anonymised data will be assimilated and shared (including in publication format) to support service development.
- We will retain anonymised data and samples long term such that material can be reused for future analyses relevant to chronic BBV infection and liver disease, subject to terms of consent and ethical permission (those who have consented for research).

Approach for all participants, after providing information:

1. Baseline data collection -
 - NHS identifiers: NHS number, name, date of birth - information to remain in clinical domain only.
 - Questionnaire (demographics, viral hepatitis and metabolic risk factors)
2. Point of care testing (POCT)* for HIV, HBV, HCV, syphilis.
3. Measurement of biometric data (weight, height, waist circumference).
4. For all those who are POCT positive, and a subset of at least 100 who are POCT negative (more if capacity allows), we will offer fibroscan assessment (non-invasive point of care test to assess liver health):
 - Transient elastography (TE) - assessment of inflammation / fibrosis
 - Controlled attenuation parameter (CAP) - assessment of steatosis
5. Venous bloods (see **table 1**)**
 - All participants:
 - Since Mongolians may be a high risk category for diabetes, (31) everyone will be offered a glycosylated haemoglobin blood test (HbA1c, in line with the NHS optimising tests in primary care document (32)). We will not test anyone with a pre-existing diagnosis of diabetes.
 - Lipid profile will be offered for those aged >40 years, BMI >23 or they have a family history of high cholesterol or heart disease (33). We will not test people already taking lipid lowering medication.
 - HBV serology for surface and core antibody, to establish if susceptible to HBV infection.
 - If HBV positive POCT: Hepatitis B surface antigen (HBsAg), HBV viral load, HBV core antibody, HBV e Antibody/Antigen, hepatitis D antibody, liver function tests.
 - If HCV positive POCT: HCV antibody, HCV RNA, liver function tests.
 - HIV positive on POCT: HIV antibody/antigen, HIV viral load.

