A WHO assessment of the OraQuick anti-HCV test (OraSure Technologies, Pennsylvania, USA) revealed sensitivity 100% (97.8% to 100.0%) and specificity 99.4% (97.3% to 99.8%) (38). Age-adjusted chronic infection prevalence is estimated to be 6% , therefore this test should not give rise to any false negatives and 3 false positive results (39).

(ii) Laboratory research domain (part 2):

7. For all those who are POCT positive, and up to ~ 100 who are POCT negative, we will offer the opportunity to enrol in research, which includes:
- o 3 additional blood tubes for research (pathogen sequencing, metabolomics, biomarkers, immune profile, host genetic sequencing).
 - All those with chronic viral hepatitis infection who consent for research will have these additional bloods.
 - For those without BBV infection, we will only collect additional bloods on:
 - o Maximum 50 of those without steatosis
 - o Maximum 50 of those with steatosis

(iii) Qualitative domain (part 3)

During the screening event, participants will be asked to indicate whether they consent to future contact to be invited into a qualitative study. We will use methods similar to those previously published, in a study which investigated barriers and opportunities to HBV testing in a UK Somali population (40). Our team brings expertise in community engagement and qualitative data collection in both primary ([name]) and secondary ([name]) care settings and working with international communities ([name]).

There will be 2-4 focus groups of 5-8 participants (number of groups will be limited by idea saturation, willing participants, time and cost). We will use purposive sampling to identify a range of community members of different ages, time in the UK, gender etc., who are likely to have a variety of views on chronic viral hepatitis testing and access to healthcare. To avoid the risk of accidental disclosure of infection status, we will only invite participants who are not living with a blood borne virus.

We will perform a semi-structured 1:1 interview of a sample (~5) people with chronic viral hepatitis to explore barriers and facilitators to diagnosis, linkage-to and retention-in-care, stigma and discrimination, and other topics relevant to chronic viral hepatitis diagnosis and management.

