In the research lab at the Francis Crick Institute, we will receive the samples on the same day. If overnight storage is required prior to processing, samples will be held at 4°C. Samples will be separated and divided into aliquots to be stored at -80°C.

The project has been reviewed by the Human Biology Scientific Technology Platform at the Crick.

Samples will be prepared and processed in batches, with primary material handled and processed within an approved Containment Level 3 facility. Samples will only leave the CL3 environment when they have been treated to inactive infectious material based on existing laboratory protocols which have been improved by internal Crick Health and Safety and external review.

Research analysis will be undertaken including:

> **HBV sequencing:** we will aim to generate HBV sequences (aiming for full viral genome) from individuals who have tested HBsAg-positive, where possible based on viral load, using a combination of methodology that includes PCR amplification, and either short-read (e.g. Illumina) and/or long-read (e.g. Nanopore) sequencing, using the most recently optimised approaches, based on existing published methods (39, 40). Sequences will be analysed to determine the genotype of HBV infection, and to identify other polymorphisms that may be relevant to disease outcome (e.g. drug and vaccine resistance, polymorphisms associated with liver cancer, polymorphisms associated with the host immune response). We will store samples for possible future sequencing of other viruses (e.g. HIV, HDV, HCV).

> **Metabolomic / Lipidomic analysis:** In collaboration with the Metabolomics Scientific Technology Platform at the Crick, lipids will be extracted from serum samples using a modified Bligh-Dyer method and analysed via Liquid Chromatography-Mass Spectrometry (41). Data and statistical analysis will be completed by experienced data analysts in the Metabolomics Science Technology Platform. We will measure metabolites and lipids in serum samples to determine the relationship between these peripheral profiles and virologic outcomes, liver fibrosis/steatosis. Ideally these samples will be fasted (6-8 hours). We will provide information on this ahead of the study, and provide refreshments after the screening, but being unfasted will not preclude participants from entering the study.

> **Measurement of a panel of host and viral biomarkers** pertaining to the development of liver disease:

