- **cytokine profile** (phenotyping host immune markers which may be relevant in outcomes of infection, using established platforms for analysis, such as O-link or MSD assay)
- **Host transcriptomic profile** (characterising host gene expression to understand differences according to metabolic factors, viral infection and fibrosis/steatosis level)
- **viral antigens** (quantification of HBV antigens including HBsAg, HBeAg, HBV core related antigen)
- **viral nucleic acids** (quantification and/or sequencing of viral DNA / RNA for any viruses detected in the sample)

> **Ascertainment of host genetic background** focusing on the MHC Class I region (HLA genes) which are known to be important determinants of immune response to vaccination and infection, but also generating information on the whole genome to undertake lineage correction.

We anticipate that most assays will be undertaken in-house at the Francis Crick Institute. However, certain assays are not available locally and we will therefore send samples to collaborating laboratories for additional tests (in the UK or internationally) such as quantification of HBV pregenomic RNA or core antigen. Any samples sent to other laboratories will be under the terms of a Material Transfer Agreement (MTA), and participant information / consent will include their permission for samples to be shipped if required. No identifying data will accompany samples shipped for research purposes.

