9 DATA ANALYSIS

We anticipate there will be 8 main groups for analysis (**Figure 4**). We anticipate groups 1-4 will be the most common groups and therefore our initial analysis will focus on these combinations.

1. Descriptive statistics will be used to describe:
 - The prevalence of HBV, HBV+HDV, HCV infection and MASLD.
 - Appropriate weighting strategies will be applied and 95% confidence intervals calculated.
 - Population demographics.
 - The burden of liver disease based on elastography, CAP scores and derangement of liver function tests, in each group (**figure 4**)
2. Comparison of liver disease severity or viral parameters between groups, to understand the impact of MASLD on chronic viral hepatitis.
 - We will look for significant differences between groups using both quantitative data, and data divided using relevant clinical thresholds (e.g. based on published definitions for liver fibrosis and cirrhosis).
 - Primary analysis will focus on a comparison between PLWHB and BBV-negative controls and participants with/without MASLD, with comparisons matched for age and sex. Secondary / subgroup analyses will be determined by the numbers of participants identified in each of our eight classes, and other relevant exposures, accounting for whether we have statistical power to interrogate the dataset for the impact of other parameters (e.g. country of birth, alcohol or smoking history, presence of metabolic syndrome).
 - Statistical tests will include Fisher's Exact Test / chi-squared for univariate analysis of binary variables, Mann-Whitney test for quantitative variables.
3. Comparison of serum lipidomic profile and cytokine analysis to explore key differences between groups and correlations with liver disease.
 - In collaboration with the bioinformatics and metabolomics scientific technology platforms at the Crick, multi-dimensional statistical modelling e.g. primary component analysis will be used to analyse results from lipidomic analysis.
4. Analysis of viral sequencing data, to identify any associations between sequence genotype and polymorphisms are associated with liver disease severity and outcomes in chronic viral hepatitis.
 - Data analysis will be in collaboration with the biostatistics and Genomics science technology platforms at the Crick. HBV sequence data will be analysed using a pipeline developed in collaboration with the ARTIC team in Birmingham (with the view to using open-source code).

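### The HDV prevalence is stated as chronic infection, but the clinical pathway measures only HDV antibody, so the planned figure would be a seroprevalence

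*Protocol*

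**What the plan says.** **What is to be estimated.** Section 3 sets the primary aim as the prevalence of chronic viral hepatitis and names HDV. Section 3.1 repeats this as "the number of people living with chronic viral hepatitis (HBV, HCV and HDV". Section 9, item 1 lists "The prevalence of HBV, HBV+HDV, HCV infection and MASLD" among the quantities to be described, with 95% confidence intervals. Section 4.5 expects about 35% of the roughly 38 people with HBV to be coinfected with HDV, about 13 people.

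**What is measured.** Section 4.3, step 5 gives the venous tests that follow a positive HBV point-of-care test. After surface antigen and HBV viral load, the list ends "HBV core antibody, HBV e Antibody/Antigen, hepatitis D antibody, liver function tests". Table 1 agrees: HDV serology is ticked for HBV-positive people, and there is no row for HDV viral load or RNA.

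**How the other viruses are handled.** For HCV the same step reads "If HCV positive POCT: HCV antibody, HCV RNA, liver function tests". HBV and HIV positives each have a viral load listed.

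**What the research laboratory may add.** Section 4.4 includes, among its biomarkers, "quantification and/or sequencing of viral DNA / RNA for any viruses detected in the sample". On sequencing it says "We will store samples for possible future sequencing of other viruses (e.g. HIV, HDV, HCV". Research blood depends on separate consent: "All those with chronic viral hepatitis infection who consent for research will have these additional bloods".

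**The concern.** The estimand is current, chronic infection; the scheduled assay detects antibody, which can persist after infection has cleared. The HCV pathway already allows for this by pairing the antibody with RNA. HDV is the only one of the three hepatitis viruses in the primary objective with no nucleic acid test scheduled, and the protocol neither explains the difference nor defines HDV infection for analysis.

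If the plan is followed as written, an anti-HDV seroprevalence will be published as a prevalence of HDV infection. The error has one direction, and neither a larger sample nor the confidence interval will reveal it. Antibody-positive, RNA-negative people would also be counted in the HBV+HDV group wherever section 9 describes liver disease burden by group. HDV prevalence is part of what the study offers to public health planning, so the label matters.

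**Working it through.** **1. Reproduce the plan's figures (section 4.5).**
- HBV: 500 × 0.075 = 37.5, stated as about 38.
- HBV/HDV: 37.5 × 0.35 = 13.1 (or 38 × 0.35 = 13.3), stated as about 13. Reproduced.
- Sample size for HBV: 1.96² × 0.075 × 0.925 / 0.025² = 426.4, rounded up to 427. Reproduced. It contains no HDV input.

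There is no arithmetic error. The issue is what the HDV count represents.

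**2. What would be reported.** If 13 people are antibody-positive, the planned estimate is 13/500 = 2.6% of those screened (exact 95% CI 1.4% to 4.4%), or 13/38 = 34% of HBV-positive people (exact 95% CI 20% to 51%).

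**3. Relation to current infection.** Let v be the share of antibody-positive people who are RNA-positive. Then current infection = antibody count × v, and the antibody figure exceeds it by 1/v. The protocol gives no v; 0.5 to 1.0 is an assumption.

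Section 4.5 does not say whether its 13 is an antibody or an RNA count, so both readings are shown:

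| v (assumed) | 1/v | If 13 are antibody-positive: currently infected, 13 × v (% of 500; % of 38) | If 13 are currently infected: antibody-positive, 13 / v |
|---|---|---|---|
| 0.5 | 2.00 | 6.5 (1.3%; 17%) | 26 |
| 0.6 | 1.67 | 7.8 (1.6%; 21%) | 21.7 |
| 0.7 | 1.43 | 9.1 (1.8%; 24%) | 18.6 |
| 0.8 | 1.25 | 10.4 (2.1%; 27%) | 16.3 |
| 0.9 | 1.11 | 11.7 (2.3%; 31%) | 14.4 |
| 1.0 | 1.00 | 13 (2.6%; 34%) | 13 |

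The ratio is the same under both readings; the counts are not. The overstatement is nil only at v = 1.

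**4. Does any other part of the protocol supply RNA for the prevalence?**
- Section 4.4, viral nucleic acids: generic, conditional on a virus having been detected, and restricted to research consenters. HDV is not named and there is no link to section 9, item 1.
- Section 4.4, sequencing: HDV appears only as possible future work on stored samples.
- Section 4.3, step 6: tests missed on the day may be collected at clinic, which refers back to the same antibody-only list.
- Section 5, follow-up: HBV-positive people are referred to specialist care, but the follow-up data described are on attendance.

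None of these makes HDV RNA available for every antibody-positive participant, or makes it the case definition.

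**The case against.** The strongest reply is that RNA may still be obtained. Section 4.4 plans viral RNA quantification in research samples, and its wording about possible future work applies to sequencing, not to quantification. NHS tests follow the hospital laboratory's own protocol, which might run RNA automatically on antibody-positive samples, and specialist clinics might do so too. A separate analysis plan could define HBV+HDV infection. Part of this stands: a reader might infer that HDV RNA is never measured in this study, and the protocol does not support that. The statement holds for the clinical pathway. But the research work is optional, not specific to HDV and not tied to the prevalence; the laboratory and clinic routes are not described as sources for it; and an analysis plan can define cases but cannot supply results that were not collected.

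The second reply concerns impact, and it stands. Section 4.5 describes the primary objective behind the sample size as HBV and HCV prevalence, so 427 is untouched. Section 9 focuses its main comparison on people with HBV against BBV-negative controls, and on presence or absence of MASLD, with other subgroups depending on numbers. A reader might infer that a planned HBV+HDV severity comparison is compromised; no such contrast is set out in the text. What remains is the descriptive burden by group.

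Third, the HCV comparison shows which tests are ordered. It does not show that the protocol defines HCV infection as RNA-positive; section 9 gives no such definition.

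**Conclusion.** The mismatch is real and confined to the HDV component. Under the clinical pathway as written, the HDV result is an anti-HDV seroprevalence among HBV-positive people, whereas the objective and section 9 call it infection. It overstates current infection by 1/v: 2.0 times at v = 0.5, 1.25 times at v = 0.8, and not at all at v = 1. The direction rests on antibody marking past as well as current infection. The size rests wholly on an assumed v and cannot be derived from the protocol.

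A reader might infer that fewer than 13 people in the plan's projection are truly coinfected. That holds only if the 13 is an antibody count. Section 4.5 presents it as coinfection; if that means current infection, 13 is the true count and the antibody-positive number would be larger, between 13 and 26 over the same range of v. A reader might also take 13 as the most samples that could need RNA testing. It is an expected count, not a ceiling: at 600 screened it becomes 600 × 0.075 × 0.35 = 15.8, and the upper limit of 51% of 38 is about 19.

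**What to change.** Reconcile the objective and the assay in one of two ways.

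1. **Relabel.** Restate the HDV part of the section 3 aim and section 3.1 objective, the section 9 prevalence and the HBV+HDV group label as anti-HDV seroprevalence among HBV-positive people. This is a text change at no cost.
2. **Measure.** If current infection is to be reported, add HDV RNA on antibody-positive samples to section 4.3, step 5 and Table 1 for outcome classification, and define HBV+HDV infection for analysis as RNA-positive. The cost is one assay per antibody-positive participant, roughly 13 at 500 screened and possibly more. Report the antibody prevalence alongside.

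Under either option, state in section 4.5 whether the 35% and the expected 13 are on an antibody or an RNA basis, so that the observed figure is compared with an expectation of the same kind. If RNA is available only for research consenters, report it as a result in that subset, with its own denominator, and not as the prevalence for everyone screened.

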4.4 Laboratory procedures

Venepuncture will be performed by a trained member of the research team. See **Table 1** for a summary of laboratory tests.

Test	All	Age ≥ 40 or BMI ≥23 [^]	HBV POCT +	HCV POCT +	HIV POCT +	Syphilis POCT +	Additional Research only	Lab
POCTs*								N/A
HBV serology [#]								NHS viro
HBV VL								NHS viro
HCV antibody								NHS viro
HCV VL & genotype								NHS viro
HDV serology								NHS viro
HIV test								NHS viro
Syphilis test								NHS viro
LFT								NHS biochem
HbA1c								NHS biochem
Lipid profile [^]								NHS biochem
Research samples [§]								UCL/ Crick

Table 1: Blood test and sample bottle required for each participant and the lab where it will be processed. All columns to the right of “All” participants indicate *additional* blood tests for participants those categories. *Point of care tests (POCTs) for human immunodeficiency virus (HIV), syphilis, hepatitis B virus (HBV), hepatitis C virus (HCV). # All participants will receive HBV core and surface antibody only to establish if susceptible to HBV infection, only HBV POCT+ will receive hepatitis B surface antigen to confirm infection. [§]Research samples for sequencing, metabolomics, biomarkers, immunology, host genetics, transcriptomics. 2 whole blood/serum or plasma and 1 PAXgene tube will be collected. [^]Only people who are not already taking lipid lowering medication will be tested. Abbreviations: HDV, hepatitis D virus; LFT, ‘liver function tests’ (Alanine Transaminase, Aspartate Transaminase, Gamma-Glutamyl Transferase, Alkaline Phosphatase, Bilirubin, albumin); HbA1c, glycated haemoglobin; VL, viral load; SST, serum separator tube; EDTA, Ethylenediaminetetraacetic acid; viro, virology; biochem, biochemistry; haem, haematology.

NHS clinical tests will be processed according to the UCLH NHS laboratory protocol.

In the research lab at the Francis Crick Institute, we will receive the samples on the same day. If overnight storage is required prior to processing, samples will be held at 4°C. Samples will be separated and divided into aliquots to be stored at -80°C.

The project has been reviewed by the Human Biology Scientific Technology Platform at the Crick.

Samples will be prepared and processed in batches, with primary material handled and processed within an approved Containment Level 3 facility. Samples will only leave the CL3 environment when they have been treated to inactive infectious material based on existing laboratory protocols which have been improved by internal Crick Health and Safety and external review.

Research analysis will be undertaken including:

> **HBV sequencing:** we will aim to generate HBV sequences (aiming for full viral genome) from individuals who have tested HBsAg-positive, where possible based on viral load, using a combination of methodology that includes PCR amplification, and either short-read (e.g. Illumina) and/or long-read (e.g. Nanopore) sequencing, using the most recently optimised approaches, based on existing published methods (39, 40). Sequences will be analysed to determine the genotype of HBV infection, and to identify other polymorphisms that may be relevant to disease outcome (e.g. drug and vaccine resistance, polymorphisms associated with liver cancer, polymorphisms associated with the host immune response). We will store samples for possible future sequencing of other viruses (e.g. HIV, HDV, HCV).

> **Metabolomic / Lipidomic analysis:** In collaboration with the Metabolomics Scientific Technology Platform at the Crick, lipids will be extracted from serum samples using a modified Bligh-Dyer method and analysed via Liquid Chromatography-Mass Spectrometry (41). Data and statistical analysis will be completed by experienced data analysts in the Metabolomics Science Technology Platform. We will measure metabolites and lipids in serum samples to determine the relationship between these peripheral profiles and virologic outcomes, liver fibrosis/steatosis. Ideally these samples will be fasted (6-8 hours). We will provide information on this ahead of the study, and provide refreshments after the screening, but being unfasted will not preclude participants from entering the study.

> **Measurement of a panel of host and viral biomarkers** pertaining to the development of liver disease:

- **cytokine profile** (phenotyping host immune markers which may be relevant in outcomes of infection, using established platforms for analysis, such as O-link or MSD assay)
- **Host transcriptomic profile** (characterising host gene expression to understand differences according to metabolic factors, viral infection and fibrosis/steatosis level)
- **viral antigens** (quantification of HBV antigens including HBsAg, HBeAg, HBV core related antigen)
- **viral nucleic acids** (quantification and/or sequencing of viral DNA / RNA for any viruses detected in the sample)

> **Ascertainment of host genetic background** focusing on the MHC Class I region (HLA genes) which are known to be important determinants of immune response to vaccination and infection, but also generating information on the whole genome to undertake lineage correction.

We anticipate that most assays will be undertaken in-house at the Francis Crick Institute. However, certain assays are not available locally and we will therefore send samples to collaborating laboratories for additional tests (in the UK or internationally) such as quantification of HBV pregenomic RNA or core antigen. Any samples sent to other laboratories will be under the terms of a Material Transfer Agreement (MTA), and participant information / consent will include their permission for samples to be shipped if required. No identifying data will accompany samples shipped for research purposes.

